## Scientific Background

Depression is the single most important contributor to suicidal ideation, attempt, and death by suicide among adolescents. Consequently, the United States Preventive Services Task Force (USPSTF) recommends that all adolescents be screened annually for major depression when formal procedures are in place to follow-up on a positive test. These recommendations have been implemented at Children's Community Pediatric (CCP) practices where adolescents who present for routine care are requested to complete the PHQ-9 depression screen on a tablet computer handed to them as a part of routine care, and embedded mental health services are present. Embedded mental health services refers to mental health services that occur within the pediatric primary care office (referring to a therapist or other mental health provider being housed within the same facility as medical providers). All practices within CCP from which this project will recruit have embedded mental health providers available, on-site. However, remaining challenges are that pediatric primary care providers (PCPs) are uncertain about how to: (1) interpret the results of screens and, (2) assess and integrate information about patient beliefs, preferences and barriers to guide their management decisions as recommended by the latest Guidelines for Adolescent Depression in Primary Care (GLAD-PC). These challenges may account for making referrals that are a less-than-ideal fit for the patient and may partially account for low rates of treatment adherence in patients who screen positive for depression. Screening Wizard aims to design and test an automated decision-support system that will provide PCPs with this information and facilitate "formal procedures to follow-up on a positive test" as recommended by the USPSTF.

## Study Objectives

Screening Wizard seeks to increase the rates of personalized referrals by PCPs among adolescents who screen positive on the PHQ-9 for depression and/or suicidal ideation at community pediatric practices by providing PCPs with decision-support recommendations that are personalized to: 1) the adolescent's symptom acuity, suicidal ideation, and comorbidities as well as 2) the adolescents' and their parents' treatment preferences, readiness for treatment, and potential barriers to following through on PCP recommendations (e.g., negative attitudes toward treatment). The goal is to provide PCPs with an opportunity to address these barriers and thereby increase the likelihood that adolescents and parents feel that their needs were met. We will collaborate with NuRelm and the Methods Core to create and rapidly iterate Screening Wizard's computerized adaptive screen, user interface, and presentation of treatment recommendations among a sample of PCPs, adolescents and their parents. NuRelm has experience with the development of behavioral health applications. Afterwards we will test the effectiveness of supplementing the PHQ-9 already administered at community pediatric practices with our tool.

Aim 1b (Phase 1b, Feasibility). To examine the feasibility of Screening Wizard in pediatric primary care clinics using a stepped wedge design. In order to enhance uptake of SW by community pediatric clinics, we will conduct the proposed work within the RE-AIM framework.

Aim 2: To examine the cost-effectiveness of Screening Wizard vs. TAU determined through service utilization of healthcare and social services.

In relation to economic analysis, we will conduct incremental cost-effectiveness analyses (CEA) to test the hypothesis that the cost per outcome achieved will be lower for adolescents exposed to ETUDES interventions (Screening Wizard is 1 of 3 interventions within the ETUDES Center) versus our treatment as usual (TAU) control condition. We will adopt a societal perspective assessing the cost of all usual health services, costs of services in other sectors (e.g., school), and costs to the families (e.g., out-of-pocket costs, missed time from work). This perspective will provide the type of data relevant to health care managers and health policy makers who would make decisions about whether or not to adopt our interventions.

We will pilot Screening Wizard in two community pediatric practices using a stepped wedge design (n=2 clinics, 50 adolescents).

Hypothesis 1b: Screening Wizard will increase the rate of personalized referrals, compared to TAU. We will perform multilevel modeling to explore time effects and intervention-level factors associated with Screening Wizard. We will first conduct t-tests for continuous variables and chi-square tests for categorical variables to examine for baseline differences in demographic and clinical variables. We will use generalized linear mixed models (nesting for site) to examine for between-intervention differences in personalized referral rate. Baseline characteristics distinguishing groups will be included as covariates in models examining treatment effects. Criterion for success: 75% of PCP recommendations partially or completely match Screening Wizard personalized referral and there is a 50% increase in number of parents and adolescents who feel their needs were met after the PCP visit during the Screening Wizard phase compared to TAU.

## **Study Design & Methods**

The information that will go into Screening Wizard will be clinical severity as determined by the patient reported PHQ-9 and Y-CAT adaptive screens for suicidal risk, anxiety and mania, screen for trauma risk and substance use history as per routine screen already performed at practices, parent perception of adolescent functioning, both parent and patient readiness for treatment, treatment preferences (antidepressants and psychotherapy), depression literacy, and adolescent and parent perceived barriers to treatment, with an estimated total time for screening of 4 minutes or less, including the PHQ-9 and adaptive screen for suicide risk. The PHQ-9 report of functional impairment and total score, and the screens for suicidal risk, anxiety, mania, and substance use provide information about acuity and the need for specialty vs. primary care location for treatment, and the attitudinal measures will shape recommendations that reflect personal preferences, readiness to engage in treatment, depression knowledge, and perceived barriers.

During TAU, PCPs will receive a PHQ-9 score and results of the suicide item. When the clinics

implement Screening Wizard, PCPs will receive reports of screening results with accompanying decision support. A one-page results sheet will be wirelessly sent to an in-office printer for the PCP to examine prior to the visit as well as integrated into the EHR. In addition, the PCP will receive psychoeducation material personalized to the parent and adolescents' preferences and concerns identified by the assessment which can be printed or electronically sent to patients and parents. For example, a PCP may receive a one-page document that lists: the patient's name and date of birth; their mental health screening results (e.g. MENTAL HEALTH SCREENING RESULTS: Depression Score (PHQ-9) = 14 – Consider Depressive Disorder, Moderate Severity, Mild functional impairment; ED Stars Suicidality Concerns: Low, Anxiety: Consider Generalized Anxiety Disorder, Mild Severity; Mania: Negative Screen; Substance Use: Negative Screen), Functioning Score (Parent Report): Moderate Problems with Functioning; a Values Results Table which categorizes the following: readiness for treatment, treatment preference, depression knowledge, identified barriers in both the adolescent and parent (e.g. adolescent and/or parent prefer therapy; adolescent identifies barriers of stigma and school/activities conflict and parent identifies barriers of stigma and insurance coverage/cost), noting any differences between the two – as issues of high concern, some concern, or no concern. In this example, all categories may be of some concern to both the adolescent and parent but the adolescent's depression knowledge is high while the parent's is medium and there, a difference is noted. Then the personalized referral recommendation will be provided based on the decision support algorithm. In this example, the PCP will be instructed to “consider referral for psychotherapy by a embedded mental health specialist and ask patient to schedule a PCP follow-up appointment to reassess if after reviewing materials, they change their mind regarding treatment preferences or have further questions.” Additionally, personalized psychoeducation materials obtained from a menu of mental health resources matched to the patients' value results will be listed and printed. These resources were gathered and approved by an expert committee including [name] through the Youth Providers 2.0 initiative funded by the Agency for Healthcare Research and Quality. In this example, these include: 1) Parental Education on Depression in Children; 2) Stigma Handout for Adolescent; for Parent; 3) Parent Guidance re: Insurance for Mental Health; 4) Adolescent-Parent Guidance on Asking for School Accommodations for Mental Health Concern. Screening Wizard helps to target the selection of materials in such a way as to potentially promote treatment initiation. In this example, the parent may realize that the patient has a conflict between attending a treatment appointment and school activities. Screening Wizard would recognize this discrepancy and provide the parent with materials about school accommodations, which might increase likelihood that the adolescent would attend treatment and the parent would be satisfied with visit.

Screening Wizard will be developed with iterative feedback from end-users (both families and PCPs) using principles of user-centered design with the assistance of the ETUDES Methods Core in conducting qualitative studies described below. A decision tree based on available evidence and expert consensus will determine personalized treatment recommendations with input from the measures as described above. The flowchart for the decision tree will be refined during the usability (phase 1a) and feasibility (phase 1b) phases of the study and will include an immediate referral to a suicidality intervention provided by the primary care clinic staff if high suicidality is identified by PHQ-9 item 9 and the adaptive suicide assessment. The decision tree will prioritize decisions as to how quickly patients should be seen, and in what sector based on suicidality, depression severity, parent perception of adolescent functioning, and presence of

comorbidities. The default treatment recommendations made based on depression severity will then be modified based on: 1) readiness for treatment and 2) treatment preference considering A) congruence between the adolescent and parent, B) depression knowledge, and C) identified barriers. We will also inquire about family history of bipolar illness. The NuReIm team and Methods Core will support integration with the Epic EHR at this stage.

In the Phase 1b, Feasibility, we will test the feasibility of using Screening Wizard in two community pediatric practices (n=50) using a stepped wedge design. We hypothesize that participants, parents, and clinicians will find the intervention usable and feasible to deploy.

To operationalize the main outcome, we will review the EHR for the treatment recommendation made by the PCP and categorize it as: 1) PCP recommendations matches Screening Wizard referral; 2) PCP recommendation partially matches Screening Wizard referral; or 3) PCP recommendation does not match Screening Wizard referral.

For example, if the Screening Wizard recommendation would be to “consider referral for psychotherapy by a embedded mental health specialist and ask patient to schedule a PCP follow-up appointment to reassess if after reviewing materials, they change their mind regarding treatment preferences or have further questions.” If the PCP treatment plan is to refer to embedded mental health specialist AND schedule a PCP follow-up appointment, this would be a match outcome; if the PCP treatment plan is to ONLY refer to embedded mental health specialist this would be a partial match outcome; if the PCP treatment plan is to start an antidepressant, this would be a does not match outcome. Additionally, we will cross-validate the Screening Wizard results in a random sample of 20% of referrals made via Screening Wizard by comparing the Screening Wizard recommendation with the recommendation made by two experts (Drs. [name] and [name]) in depression treatment.

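### The main-outcome match is rated from an EHR that also holds the Screening Wizard report, with no separation of recording the PCP plan from judging the match, so ambiguous plans may be rated differently by phase

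*Combined protocol and SAP*

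**What the plan says.** All of the following is in the combined protocol and SAP.

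- **Source of the rating (Study Design & Methods).** For the main outcome, "we will review the EHR for the treatment recommendation made by the PCP and categorize it as" one of three levels. The middle one is "PCP recommendation partially matches Screening Wizard referral".
- **Where the report goes (same section).** In the Screening Wizard phase a one-page sheet is printed "for the PCP to examine prior to the visit as well as integrated into the EHR". After the screening results and values table, "Then the personalized referral recommendation will be provided based on the decision support algorithm".
- **TAU phase (same section).** "During TAU, PCPs will receive a PHQ-9 score and results of the suicide item". No Screening Wizard report is described for this phase.
- **Coding rule (same section).** There is one worked example, in which the tool suggests embedded psychotherapy plus a PCP follow-up visit. Doing both is a match; "if the PCP treatment plan is to ONLY refer to embedded mental health specialist this would be a partial match outcome"; starting an antidepressant is no match.
- **Quality check (same section).** "we will cross-validate the Screening Wizard results in a random sample of 20% of referrals made via Screening Wizard", by comparing the tool's recommendation with that of two experts.
- **Use of the rating (Study Objectives; Statistical Considerations).** Hypothesis 1b compares the personalized referral rate between Screening Wizard and TAU. The success criterion has two joint parts: 75% of recommendations match partially or completely, and needs met rises by 50% over TAU.

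The documents do not say who rates. They describe no masking to phase, separate abstraction, duplicate rating or agreement statistic.

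**The concern.** The outcome is a judgement, and the record it is read from differs by phase in a way that bears on that judgement. In the Screening Wizard phase the rater can find the tool's recommendation in the same chart as the PCP plan. In TAU, on the description given, no such report exists. Its presence therefore marks the phase and supplies a reading of the plan at the moment the plan is being interpreted.

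This matters most where a plan is ambiguous. The worked example fixes one plan per category for one recommendation. It does not settle, for instance, a PCP follow-up visit without a referral, or therapy arranged outside the practice. Because partial matches count toward the 75%, the line between partial match and no match decides that component. If doubtful plans are read more generously in one phase than in the other, both the Hypothesis 1b comparison and the 75% component move for reasons unrelated to what PCPs did.

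The 20% expert check would not reveal this. It tests the algorithm's recommendation against expert opinion, only for Screening Wizard referrals, and does not re-rate the match.

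**Working it through.** **The plan's own figure.** The only stated precision is a 95% CI width of at most 0.28 at n = 50 (Statistical Considerations). The Wald full width at p = 0.5 is 2 × 1.96 × √(0.25/50) = 0.277, which reproduces it. That figure covers sampling error only. It is not disputed, and rating error would add to it.

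**The passages side by side.** (a) The rating is made from the EHR. (b) The sheet carrying the recommendation is in the EHR during the Screening Wizard phase. (c) In TAU the PCP gets only the PHQ-9 score and suicide item. From (a) to (c), a rater following the procedure as written can tell the phase and can see the recommendation while reading the plan. That the rater does so is an inference, since neither the rater nor the way charts are presented is described.

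**Size, as an illustration.** The documents give no phase split, expected match rate or rating-error rate, so every input below is an assumption:

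- n = 25 Screening Wizard visits (half of 50); 0.75 × 25 = 18.75, so 19 matches are needed;
- p = true partial-or-complete match rate, central value 65%;
- u = share of true non-matches upgraded, in the Screening Wizard phase only; no errors in the other direction; visits independent.

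Observed rate = p + u(1 − p). Spurious between-phase difference, if the true rate is equal in both phases = u(1 − p). Chance of meeting the 75% component = P(X ≥ 19), X ~ Binomial(25, observed rate).

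| True rate | u | Observed rate | Spurious difference | P(X ≥ 19) |
|---|---|---|---|---|
| 65% | 0 | 65.0% | 0 | 17% |
| 65% | 10% | 68.5% | 3.5 points | 28% |
| 65% | 20% | 72.0% | 7.0 points | 42% |
| 65% | 30% | 75.5% | 10.5 points | 58% |
| 60% | 0 | 60.0% | 0 | 7% |
| 60% | 20% | 68.0% | 8.0 points | 27% |
| 70% | 0 | 70.0% | 0 | 34% |
| 70% | 20% | 76.0% | 6.0 points | 61% |

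Example row: 0.65 + 0.20 × 0.35 = 0.72.

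**Sensitivity to the number of visits** (true rate 65%, u = 20%): with 20 visits (15 needed) the chance goes from 25% to 50%; with 30 visits (23 needed), from 12% to 37%.

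**In counts.** With 17 of 25 rated as matches, the component fails at 68%. Upgrading 2 of the 8 non-matches gives 19 of 25, or 76%, and it passes.

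**Errors in both directions.** At a true 65%, upgrading 20% of non-matches adds 0.20 × 0.35 = 7 points. Downgrading 7/65 = 10.8% of true matches removes the same 7 points and leaves the observed rate at 65%. The net effect depends on the balance of errors, which the documents do not inform.

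**The case against.** **Any match rating has to use the recommendation.** This stands. Agreement with the Screening Wizard referral is the outcome, so whoever or whatever assigns the category needs that referral in both phases. A reader might infer that knowing the target answer is itself the flaw; it is not. The weakness is narrower: recommendation and phase are visible while the PCP plan is still being interpreted.

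**The rater is not stated to be unmasked.** Also true. The documents are silent on the rater, and they say what PCPs receive in TAU, not what the TAU chart holds. It would go too far to state that the rater knows the phase. What can be said is that the procedure described would show it and nothing described prevents that.

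**The coding is action-based.** The worked example uses discrete actions, which limits discretion. It covers one recommendation and one plan per category, however, so other combinations remain open.

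**The direction and size are assumed.** This stands. A reader might infer that the match rate will be inflated and the pilot wrongly declared a success. The documents support neither. Upward bias is plausible, not shown, and opposite errors could cancel it. The match rate is one of two joint criteria, and needs met is not rated from the EHR, so the probabilities above are not chances of overall success.

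**It is a small feasibility pilot.** This limits the weight of the point but does not remove it. The plan sets an explicit 75% threshold, and with 50 adolescents in two clinics a couple of ratings can decide it.

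**Conclusion.** The point holds in a limited form. The plan rates its main outcome from a record that, in the Screening Wizard phase, contains the tool's recommendation. It does not separate abstraction from matching, gives one worked example as its rule, and has no check on the rating itself. Ambiguous plans may therefore be classified differently by phase, which would affect the Hypothesis 1b comparison and the 75% match component.

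The actual size and direction cannot be estimated from the documents. Under the assumed inputs (25 visits, true rate 65%, upgrading only), upgrading 10% to 30% of non-matches raises the chance of meeting that component from 17% to between 28% and 58%, and creates a spurious difference of 3.5 to 10.5 points. The documents do not support a claim that the results will be biased upward or that the overall success decision will be wrong. No sample-size figure changes. The change is worth making because it is cheap and the threshold is sensitive to a few ratings.

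**What to change.** Split the rating into two steps.

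1. **Abstract.** The same abstractor records the PCP plan from the visit note into fixed yes/no action fields (for example embedded psychotherapy referral, specialty referral, antidepressant, PCP follow-up), without opening the Screening Wizard report, and locks the form.
2. **Match.** One written coding rule, fixed before abstraction starts, is applied by script in both phases to assign match, partial match or no match against the algorithm's recommendation.

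Two conditions must be written in for step 2 to work:

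- **A recommendation for TAU patients.** The documents do not say how one is obtained. For scoring, it must be generated from the same inputs as in the Screening Wizard phase, without being shown to the PCP. The plan should say whether those inputs are collected during TAU.
- **One decision-tree version.** Study Design & Methods says the tree will be refined during phase 1b. One fixed, recorded version should score all patients, so that the target does not shift between phases.

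**Cost.** A short abstraction form, a short script and a rule agreed in advance, with no extra abstractor. If the TAU inputs are not already collected, obtaining them is an added burden that the documents do not allow one to size. Notes and visit dates may still reveal the phase, so masking is partial; fixed fields and a mechanical rule leave less room for that knowledge to alter the category.

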## **Eligibility Criteria**

### **Youth Inclusion Criteria:**

- Youth aged 12-26 yo
- Biological or adoptive parent is willing to provide informed consent for teen to participate
- Youth speaks and understands English

### **Youth Exclusion Criteria:**

- Non English speaking
- No parent willing to provide informed consent
- Is currently experiencing acute mania or psychosis, evidence of an intellectual or developmental

disorder (IDD), life threatening medical condition that requires immediate treatment, or other cognitive or medical condition preventing youth from understanding study and/or participating.

## **Statistical Considerations**

A stepped wedge design was selected for both ethical considerations and feasibility. A stepped wedge cluster randomized trial design involves the sequential random rollout of an intervention over multiple time periods following a “baseline” period when no cluster has been exposed. The crossover is typically in one direction, from control to intervention, and continues until all of the clusters receive the intervention with observations taken from every cluster and at each time period. All 3 studies in the ETUDES Center, and specifically, Screening Wizard, will utilize this design. Prior to study start, each CCP study practice will be randomly assigned to switch from Treatment As Usual (TAU) to the intervention.

In the proposed stepped wedge design, all practices start with TAU (i.e., PCP referral to embedded MH care) and are randomized to transition to implement Screening Wizard at different times. All clinics will be initially monitored for at least 2 months during TAU, followed by a staggered adoption of Screening Wizard. During each time period, a new clinic will begin to use Screening Wizard (order determined by block randomization). A web-based system will randomly assign the next clinic to begin.

Hypothesis 1b: Screening Wizard will increase the rate of personalized referrals, compared to TAU. We will perform multilevel modeling to explore time effects and intervention-level factors associated with Screening Wizard. We will first conduct t-tests for continuous variables and chi-square tests for categorical variables to examine for baseline differences in demographic and clinical variables. We will use generalized linear mixed models (nesting for site) to examine for between-intervention differences in personalized referral rate. Baseline characteristics distinguishing groups will be included as covariates in models examining treatment effects. Criterion for success: 75% of PCP recommendations partially or completely match Screening Wizard personalized referral and there is a 50% increase in number of parents and adolescents who feel their needs were met after the PCP visit during the Screening Wizard phase compared to TAU.

Due to the pilot nature of this study, sample size and power considerations center around the precision of confidence interval (CI) width estimation for feasibility outcomes. In the Development Phase (Aim 1), a sample size of 50 affords us a 95% CI width of no more than 0.28.

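### The model for the Screening Wizard versus TAU comparison names site but not calendar period, and this one-way, two-clinic roll-out has no period-adjusted estimate committed beside it

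*Combined protocol and SAP*

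**What the plan says.** The Hypothesis 1b paragraph appears under Study Objectives and again under Statistical Considerations. It gives one model for the SW-TAU difference: "We will use generalized linear mixed models (nesting for site) to examine for between-intervention differences in personalized referral rate". The covariate rule is: "Baseline characteristics distinguishing groups will be included as covariates in models examining treatment effects". Time enters the analysis text once, in a separate sentence: "We will perform multilevel modeling to explore time effects and intervention-level factors associated with Screening Wizard".

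The size of the design is given under Study Objectives: "We will pilot Screening Wizard in two community pediatric practices using a stepped wedge design (n=2 clinics, 50 adolescents". Statistical Considerations describes the roll-out in general terms ("The crossover is typically in one direction, from control to intervention, and continues until all of the clusters receive the intervention") and for this trial: "All clinics will be initially monitored for at least 2 months during TAU, followed by a staggered adoption of Screening Wizard". The pace of the roll-out, one switch per step, is set next: "During each time period, a new clinic will begin to use Screening Wizard". On sample size it states that "sample size and power considerations center around the precision of confidence interval (CI) width estimation for feasibility outcomes".

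**The concern.** Within each clinic, every SW youth is seen later than every TAU youth. The staggered switch helps to separate SW from calendar time only if the analysis uses period. The one model named for the comparison does not name it. Period is also not a baseline characteristic of the youths, so the covariate rule does not bring it in.

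If referral habits or season shift in both clinics during the roll-out, an estimate without period counts that shift as SW effect, and its confidence interval is centred on the wrong value. One possible source is in the plan itself. Study Design & Methods says that the decision tree will still be refined during the feasibility phase, and the outcome is agreement with that tree's referral. The documents do not say whether this would act as a trend common to both clinics. At stake are the reported Hypothesis 1b estimate and any later trial planned from it.

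**Working it through.** **Inputs from the documents.** Two clinics and 50 adolescents; all start on TAU; one clinic switches per period. With two clinics this implies at least three periods (TAU/TAU, SW/TAU, SW/SW). The number is not stated.

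**Assumptions, not in the documents.** Exactly three periods, numbered 0, 1, 2; cell counts 8, 8, 9 in clinic A (first to switch) and 9, 8, 8 in clinic B, so 25 TAU and 25 SW; a 50% rate in the middle period; no SW effect; linear drift *d* per period, common to both clinics.

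**1. The plan's own figure.** 2 × 1.96 × √(0.5 × 0.5 / 50) = 0.277, which agrees with the stated maximum width of 0.28. It concerns one proportion in all 50 youths and does not depend on this point.

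**2. Clinic fixed, no period.** The estimate averages the two clinics' own after-minus-before differences, weighted by n(TAU) × n(SW) / n. The weights are 8 × 17 / 25 = 5.44 in A and 17 × 8 / 25 = 5.44 in B, so they are equal and sum to 10.88.
- SE at p = 0.5: 0.5 / √10.88 = 0.152.
- Drift in A: mean SW period (8 × 1 + 9 × 2) / 17 = 1.53, mean TAU period 0; difference 1.53.
- Drift in B: mean SW period 2, mean TAU period 8 / 17 = 0.47; difference 1.53.
- The false effect is therefore 1.53*d*: 8, 15 and 23 points at *d* = 5, 10 and 15.

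**3. Period added.** The cell weights become A (−0.5, +1, −0.5) and B (+0.5, −1, +0.5), so common drift cancels and the bias is 0.
- Sum of weight²/n: 2 × 1/8 + 0.25 × (1/8 + 1/9 + 1/9 + 1/8) = 0.368.
- SE: 0.5 × √0.368 = 0.303.
- t-based 95% half-width: 0.611 (45 df), against 0.305 (47 df) without period.

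**4. Simulation.** Linear models: 40,000 trials per row. Random-intercept logistic model with likelihood-ratio test: 1,500 trials per row. A second GLMM run of 1,000 trials per drift gave mean false effects of about 7, 15 and 21 points.

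| Drift per period (points) | False effect, clinic fixed | False effect, random-site GLMM | CI miss, no period | GLMM rejection | CI miss, with period | RMSE, no period | RMSE, with period |
|---|---|---|---|---|---|---|---|
| 0 | 0 | 0 | 5.2% | 5.9% | 5.1% | 0.151 | 0.302 |
| 5 | 8 | 6-7 | 8.6% | 9.5% | 5.2% | 0.169 | 0.302 |
| 10 | 15 | 15 | 18.1% | 18.8% | 5.3% | 0.213 | 0.300 |
| 15 | 23 | 21 | 34.7% | 36.1% | 5.8% | 0.273 | 0.300 |

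**5. Other layouts.** Over five three-period allocations the bias per unit of drift is 1.3-1.7. Over three four-period layouts it is about 2.04, but that counts drift per period. As a share of the first-to-last drift it is 2.04 / 3 = 0.68, against 1.53 / 2 = 0.76 with three periods, so four periods are not worse.

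**6. Limits of the period-adjusted estimate.**
- The RMSEs are equal at √(0.303² − 0.152²) / 1.53 = 0.171. Below about 17 points of drift per period the estimate without period is closer to the truth by RMSE.
- Half of the absolute weight (2 of 4) is on the 16 middle-period youths.
- A change in clinic A in the middle period only biases it by 1.0 times the change, against 0.24 without period. For a 30-point dip the CIs miss in 16% against 8% of trials.
- A lasting change in clinic A from the middle period on biases both by 0.5 times the change.
- With a clinic-by-period SD of 0.10, both CIs miss in 9%.
- At 40% versus 75% without drift, power is 24% with period and 68% without; wrong-sign estimates are 11% and 1%.

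**The case against.** The sentence on exploring time comes just before the GLMM sentence, under the same hypothesis, and a GLMM is a multilevel model. A reader might infer that the plan ignores time, or has deliberately chosen a before-after analysis. The documents do not support that: the two sentences may describe one strategy. What stands is that, even on this generous reading, no sentence says that period enters the SW model, in what form, or that an adjusted SW estimate will be reported.

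Second, site nesting suggests a random site, and the clinic-fixed figures of 8, 15 and 23 points slightly overstate its bias. In the 1,000-trial GLMM run the fitted site SD was essentially zero in 84-88% of trials, so the fit was close to a pooled comparison of 25 with 25 youths. It is therefore mainly, not purely, a within-clinic contrast. Confounding with time remains.

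Third, all of the harm depends on assumed drift. At 5 points per period the CI misses in 9% against 5% of trials, and the estimate without period has the smaller RMSE at every drift in the table. A reader might infer that the period-adjusted model should replace the planned one. Its limits in step 6 speak against that, and neither model is safe as the only answer.

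Fourth, this is a pilot with no power claimed for the comparison. That limits the weight of the point but does not remove it: Hypothesis 1b is comparative, and an estimate will be reported.

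**Conclusion.** The concern holds as a minor to moderate point. The plan's model for the SW-TAU difference names site and baseline covariates but not period, and exploring time commits to no period-adjusted estimate. In a one-way roll-out over two clinics, an estimate without period is mainly before-after and takes up any common trend. Under the stated assumptions, drift of 5, 10 or 15 points per period produces a false effect of about 6-7, 15 and 21 points in the random-site GLMM, with CI miss or rejection of about 9%, 18% and 35%. With no drift there is no bias.

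A reader might infer that the pilot's go-ahead decision is compromised. It is not, on this ground: the success criteria (the share of recommendations that match, and the change in families who feel their needs were met) are not read off this model, and neither is the 0.28 width. The harm is limited to the Hypothesis 1b estimate and planning from it. The three periods, the cell sizes, the base rate and the drift are all assumptions.

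**What to change.** After the GLMM sentence in both copies of the Hypothesis 1b paragraph, add wording to this effect:

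> The SW-TAU risk difference for match or partial match versus no match will be reported from two linear models. Both contain SW status, clinic as a fixed effect and the same baseline covariates, if any, with a t-based 95% CI. The second also contains calendar period, bounded by the actual crossover dates, as a categorical fixed effect. The first will be labelled a before-after estimate that assumes no time trend, the second an estimate that assumes a trend common to both clinics. Both are descriptive. Match counts will be tabulated by clinic and period.

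Keeping the two models otherwise identical means that any difference between them is due to period alone, not to link, site handling or covariates. The planned GLMM and the success criteria stay as written.

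The cost is plan wording, two estimates and one small table, with no new data, visits or youths. The downside should be stated in the report. The period-adjusted CI is about twice as wide, rests largely on the middle period, has the larger RMSE until drift reaches about 17 points per period, and gives no protection against a change in one clinic only. Readers will see two estimates that may differ.
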